8.2. Minimization of Risks

Potential risks associated with the use of the GORE® Carotid Stent may be minimized by the following activities:

- The Sponsor has performed qualification testing on the device and device components and appropriate quality control measures have been implemented into production.
- Investigators will be selected who are knowledgeable and experienced in carotid artery stenting procedures.
- Comprehensive Site Investigator and staff training will be conducted to share information regarding design and proper use of the GORE® Carotid Stent.
- The Site Investigator, Sub-Investigators, Clinical Study Coordinator(s) or designee at each Site will be trained to the protocol and Subject follow-up requirements.
- Protocol inclusion/exclusion criteria and follow-up schedules are designed to select appropriate subjects and identify potential complications early.
- Subjects will be assessed post-procedure and subsequently on a regular basis to collect information on the subject's status and any reportable adverse events.
- Data completed by the Sites will be monitored to evaluate protocol compliance and the data for accuracy and subject safety.
- Safety and efficacy data obtained during the clinical study will be shared with the Site Investigators to aid understanding of the device and potential complications associated with its use.

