5.5. Pre-Screening/Screening

All patients who sign an ICF will be considered entered into the screening phase of the study.

A subject screening log will be maintained at each site to document select information about the patients who sign informed consent. For patients who did not meet eligibility criteria **after** signing informed consent, the reasons for exclusion will be documented on the subject screening log.

The following evaluations will be conducted at the **screening visit** or must have been completed no more than 30 days prior to enrollment (except as noted):

• Informed consent (prior to any study related procedures being performed)

GORE CONFIDENTIAL INFORMATION

- Inclusion and exclusion criteria assessed; confirmation is required by Screening Committee
- Assess medical history, demographics, and concomitant medications
- Modified Rankin Scale
- 12-lead ECG
- Examination and vital signs
- Chemistry (BUN & Creatinine)
- Hematology (CBC including platelets)
- Bilateral Carotid Duplex Ultrasound (within the 60 days preceding the index procedure)
- Angiography (within 30 days) and/or CTA (within 60 days)
- CT or MRI Brain Imaging for symptomatic patients only (Within 180 days of the index procedure)I

Pre-screening Assessment

A Screening Committee will review pre-operative angiography and/or CTA, along with patient medical history, for assessment of entry criteria, and approval prior to the study procedure.

The Screening Committee will be comprised of an interdisciplinary team of study investigators with pertinent knowledge in carotid stenting. The members will not review potential cases from their own sites. The members will be compensated for their involvement in the Screening Committee, including reimbursement for reasonable travel expenses to attend meetings.

This committee will operate under pre-specified procedures as outlined in the Screening Committee Charter.

Prior to a patient being enrolled in the study, the investigational site must receive confirmation from the Screening Committee that the subject is eligible to be enrolled. Although patient may be deemed eligible to be enrolled, it is still the responsibility of the investigator to assess all inclusion and exclusion criteria prior to enrollment.

Screening Angiogram and/or CTA

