9.4. Clinical Events Committee

An independent Clinical Events Committee (CEC) will review potential primary endpoint events and adjudicate events based on endpoint definitions in the study protocol. The CEC will be comprised of an interdisciplinary team with pertinent knowledge in carotid stenting or the cardiovascular and/or nervous system who are not directly involved in the conduct of the study. The members will be compensated for their involvement in the CEC, including reimbursement for reasonable travel expenses to attend meetings.

This committee will operate under pre-specified procedures as outlined in the CEC Charter. The adjudication process will be initiated after a potential primary endpoint event is reported by the site.

10. Statistical Analysis

[figure not shown]

[figure not shown]
CONFIDENTIAL INFORMATION MD133246 Protocol Template Revision#: 1 Doc Type: GC

GORE® Carotid Stent MD134865 GCS 10-08 PROT Revision#: 3 Doc Type: SP

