#### 4.2.2 Staged Analysis

In accordance with the IDE approval letter from FDA dated December 13, 2012, the Gore SCAFFOLD Clinical Study was initially limited to enrollment of 100 subjects, with the following interim analysis requirement:

[figure not shown]
"Your IDE application has been approved as a staged study. You may request approval to expand enrollment in your study when you have submitted an IDE supplement which provides the 6-month results from the first 50 patients enrolled."

Thus, when the 6-month follow-up evaluation is completed (or final 6-month follow-up status determined) for the first 50 subjects enrolled, the data for these 50 subjects will be analyzed and results presented for safety and efficacy endpoints measured at procedure, 30 days and 6 months.

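### Protocol 8.2 places no limit on sharing efficacy data with Site Investigators during the study, and nothing supplied keeps pooled MAE results from those who select patients and report events

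*Protocol*

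**What the plan says.** Protocol 8.2 opens its list with "Potential risks associated with the use of the GORE® Carotid Stent may be minimized by the following activities", and the last item is that "Safety and efficacy data obtained during the clinical study will be shared with the Site Investigators to aid understanding of the device" and its possible complications. It does not say when data are shared, whether they are pooled, or which endpoints are covered.

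The recipients have three roles that feed the primary endpoint:

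- **Selection.** Under Protocol 5.5, committee approval is needed, but "it is still the responsibility of the investigator to assess all inclusion and exclusion criteria prior to enrollment". Under Protocol 5.8, a patient in whom the stent is not attempted is a screen failure and is not enrolled.
- **Approval.** Also in 5.5: "The Screening Committee will be comprised of an interdisciplinary team of study investigators with pertinent knowledge in carotid stenting". One limit applies: "The members will not review potential cases from their own sites".
- **Reporting.** Protocol 9.1.3 makes the site investigator responsible for reporting adverse events. Protocol 9.4 adds: "The adjudication process will be initiated after a potential primary endpoint event is reported by the site".

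Protocol 9.3 gives periodic review of aggregate data to the DSMB but states no confidentiality rule for those data. SAP 4.2.2 describes a staged look. Enrolment "was initially limited to enrollment of 100 subjects", and once the first 50 subjects have 6-month status their data are analysed, with "results presented for safety and efficacy endpoints measured at procedure, 30 days and 6 months". Protocol 10.4.1 and SAP 5.0 plan no interim test of the hypotheses.

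**The concern.** The study has no concurrent control. In a randomized comparison, a change in case mix during the study affects both arms. Here it moves the MAE rate directly relative to a fixed number. The same is true of a change in the threshold for reporting a possible minor stroke or MI.

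A usual protection is that the people who choose patients and report events do not know the pooled result. The plan does not state that protection, and the wording of 8.2 runs the other way. The entry criteria leave room for case mix to move without any deviation, because one high-risk condition from a list of 17 (7 anatomic, 10 co-morbid; Protocol 4.2) is enough. At stake is whether a pass or a fail against the goal reflects the device or a change in who was treated and what was reported.

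**Working it through.** **Step 1. Does 8.2 mean sharing during the study?** The sentence gives no timing. It stands in a list of activities meant to reduce risk from use of the device, and sharing can do that only while subjects are still being treated or followed. Some sharing before the primary analysis is therefore the natural reading. The level of aggregation stays open.

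**Step 2. Does another passage restrict it?** Protocol 5.5, 9.3, 9.4, 10.4.1 and 11.2 and SAP 3.3, 3.4, 4.2.2 and 5.0 were set beside 8.2. None keeps pooled MAE or efficacy results from investigators or Screening Committee members. The DSMB, CEC and Screening Committee charters were not supplied.

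**Step 3. How much enrolment follows the staged summary?** The inputs are the planned 312 subjects (Protocol 3.1) and the cap of 100 until expansion is approved on the 50-subject data (SAP 4.2.2).

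- 312 − 100 = 212
- 212 / 312 = 67.9%

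At least 212 subjects are enrolled after that summary exists, if the study reaches 312. This counts subjects enrolled after the results exist, not after any disclosure.

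**Step 4. How sensitive is the primary test to a small drift?** This is an illustration only. The test level reproduces: 1 − 0.951 = 0.049. The performance goal, expected rate and power are not visible in the public copy, so goals p0 of 10% to 20% are assumed, with all 312 subjects evaluable. The rule in Protocol 10.4.5 passes when

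x/312 + 1.655 × √(p0(1 − p0)/312) < p0.

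Example with p0 = 15%: the standard error is √(0.1275/312) = 0.0202. The limit is 312 × (0.15 − 1.655 × 0.0202) = 36.4, so at most 36 events pass.

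The table gives the exact binomial probability of passing when the true rate in the initial case mix equals the goal. The middle columns lower the risk in the later 212 by an assumed relative amount and leave the first 100 at the goal. The last column assumes that two events go unreported.

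| Assumed goal | Max events | No influence | 5% lower | 10% lower | 20% lower | 2 unreported |
|---|---|---|---|---|---|---|
| 10% | 22 | 0.045 | 0.067 | 0.097 | 0.186 | 0.100 |
| 13% | 30 | 0.041 | 0.065 | 0.100 | 0.209 | 0.084 |
| 15% | 36 | 0.048 | 0.078 | 0.121 | 0.257 | 0.092 |
| 17% | 42 | 0.053 | 0.088 | 0.140 | 0.302 | 0.097 |
| 20% | 50 | 0.043 | 0.078 | 0.132 | 0.308 | 0.078 |

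A relative 10% at these goals is 1 to 2 points in the later 212, or 0.68 × 1 to 0.68 × 2 = 0.7 to 1.4 points overall. The table shows that the test is sensitive to small drifts. It does not show that a drift of any size is likely.

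**The case against.** The strongest reply is that 8.2 is a training statement and the plan has several protections:

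- SAP 2.2.1 calls for consecutive enrolment.
- Entry criteria are fixed, and exclusions after consent are logged with reasons (Protocol 5.5).
- Committee members do not review cases from their own sites.
- NIHSS is scheduled and done by certified assessors, and ECG and troponin are scheduled after the procedure.
- Monitors review case report forms and source documents.
- An independent CEC adjudicates, and death leaves little room for discretion in reporting.

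All of this stands and lowers the risk. It does not close the route, because the CEC acts on what sites report and because selection within the criteria remains a judgement.

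Four stronger readings are tempting, and the documents do not support them:

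- *That the protocol commits to circulating a running MAE rate.* It mentions no rate and no aggregation.
- *That investigators will receive the 50-subject results.* SAP 4.2.2 ties them to an IDE supplement and names no investigator recipient. Fifty subjects also give a weak signal: an assumed 5 events in 50 has an exact 95% interval of about 3% to 22%.
- *That drift could not be seen.* Baseline risk factors are summarized, the endpoint is shown by site, and it is also analysed controlling for age, sex and race/ethnicity. A shift in recorded factors could be examined, although no comparison of earlier with later subjects is planned.
- *That patients who qualify on age alone are the lower-risk ones.* Protocol 4.2 lists age 75 or over as a high-risk condition, and nothing says these patients have fewer events with stenting.

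Two further objections carry some weight. MAE is itself the main safety outcome, and Protocol 11.2 and 11.3 require new material information to reach investigators and subjects. A blanket ban would conflict with those sections, so the fix needs an explicit exception. The charters may also contain a restriction. If they do, the unqualified sentence in 8.2 would contradict them and would still need correcting.

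**Conclusion.** The point holds as a gap in wording with a real but unquantified consequence. Read as written, 8.2 permits pooled efficacy and MAE results to reach the people who select patients, staff the Screening Committee and trigger adjudication, and no supplied passage prevents it. A summary of that kind will exist before at least 68% of subjects are enrolled. The sentence also covers every later summary up to the primary analysis.

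A reader might go on to infer that bias will occur, or that it will be a certain number of points. The documents support neither. The drift sizes and goals in the table are assumptions, and the table also assumes that all 312 subjects are evaluable. The conclusion itself rests only on the text: the unlimited sentence in 8.2, the investigators' roles, and the absence of a restriction. It is an inexpensive improvement and does not invalidate the design.

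**What to change.** Replace the last item in Protocol 8.2 with wording to this effect:

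> During the study, Site Investigators will receive device-handling information, individual event reports, DSMB recommendations, and any new safety information needed to protect subjects, consistent with Sections 11.2 and 11.3. Pooled primary-endpoint (MAE) rates and other efficacy summaries, including the staged results from the first 50 subjects, will not be provided to Site Investigators or Screening Committee members until the primary endpoint analysis is complete, unless the DSMB recommends release for subject safety.

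Add a matching sentence to SAP 4.2.2 that names who receives the staged results, and check that the DSMB and Screening Committee charters agree.

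The cost is a protocol wording change and a distribution list. The sample size of 312, the test level of 0.049 and the visit schedule do not change. The downside is that investigators see aggregate results later.

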8.3. Summary of Expected Benefits

The GORE® Carotid Stent is expected to be safe and effective when used to treat stenosis of the carotid artery. The intent is to increase blood flow to the brain while decreasing the narrowing in the artery, and to help prevent future strokes.

9. Adverse Events and Safety Monitoring

Adverse Events (AEs) are defined as any untoward medical occurrences in a subject whether device-related or not.

9.1. Anticipated Adverse Events

Anticipated Adverse Events are complications that are known to be associated with carotid artery stenting. Potential complications of carotid artery stenting are listed in Section 8 above. If a complication occurs that is not on the list of known, potential complications and the investigator believes that the complication is a potential UADE (Unanticipated Adverse Device Effects, see section below), the site should immediately contact the Sponsor to determine reporting requirements.

Anticipated Adverse Events are complications that are known to be associated with carotid artery stenosis patients undergoing an angioplasty and stenting procedure. See Section 8, Risk Assessment.

9.1.1. Adverse Event Relationship

Each reported AE will be assessed by the Investigator for its primary suspected relationship to the carotid stent, embolic protection device, procedure, medication, or disease. Only one primary relationship will be assigned to each reported AE.

Study Device-related

The functioning or characteristics of the device caused or contributed to the Adverse Event.

Embolic Protection System (EPD)-related

The functioning or characteristics of the EPD caused or contributed to the Adverse Event.

Study Procedure-related

The study index procedure (and not the device or EPD) caused or significantly contributed to the Adverse Event.

Medication-related

The Adverse Event was a result of medical therapy prescribed by the study protocol and not the device, EPD, or procedure.

Disease-related

The Adverse Event was a result of the underlying disease progression for which the study procedure is being performed, and not the device, EPD or procedure.

Not related

An Adverse Event which cannot be attributed to the device, EPD, procedure, medication or disease.

Unknown relationship

The relationship of the Adverse Event to the device, EPD, procedure, medication or disease cannot be determined.

9.1.2. Adverse Event Classification

Each AE will be assessed by the Investigator to determine if it is a Serious Adverse Event as defined below:

Serious Adverse Event

A Serious Adverse Event is an adverse event that

- led to death
- led to serious deterioration in the health of the subject that either resulted in
 - o a life threatening illness or injury, or
 - o a permanent impairment of a body structure or body function, or
 - inpatient or prolonged hospitalization, or
 - medical or surgical intervention to prevent life threatening illness or injury or permanent impairment to a body structure or a body function
- led to fetal distress, fetal death or a congenital abnormality or birth defect.

9.1.3. Adverse Event Reporting and Coding

AEs will be reported on the appropriate case report form (CRF) for that visit and documented in the subject's permanent medical record. The Investigator at each Site is ultimately responsible for reporting AEs to the Sponsor.

The following information on each reported Adverse Event will be collected:

- Adverse Event Name
- Adverse Event Onset Date
- Relationship
- Classification Serious
- Treatment
- Outcome
- Resolution Date

Adverse Events will be coded using the Medical Dictionary for Regulatory Activities (MedDRA).

Adverse event submission guidelines:

- Adverse event reporting begins once the patient is enrolled in the study. All adverse events should be reported from enrollment through study completion/discontinuation.
- Provide a diagnosis if possible. If unable to provide diagnosis, report the symptoms as separate events. Adverse Events should be reported using the full name without abbreviations or narratives.
- Adverse events with an outcome status of "Ongoing" should be assessed at each follow-up evaluation to determine if the event has resolved. Adverse events ongoing at study completion/discontinuation should be left as "Ongoing" on the AE case report form.

9.1.4. Subject Death

If a subject dies while participating in the study, the cause of death will be reported as the adverse event and "death" reported as the event outcome on the AE case report form. If the subject has other ongoing adverse events at the time of death, the outcome status of those events should be reported as "resolved" on the AE case report form.

The Investigator should obtain all medical records including death certificate and autopsy report for inclusion in reporting to the Clinical Events Committee.

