3.2. Study Endpoints

3.2.1. Definitions

Stroke: An acute neurologic event with focal symptoms and signs, lasting for 24 hours or more.

Minor Stroke: A stroke that resolves completely within 7 days or increases the NIHSS by < 4 points.

Major Stroke: A stroke that persists after 7 days and increases the NIHSS by \geq 4 points.

Ipsilateral Stroke: A stroke affecting the cerebral hemisphere supplied by the carotid artery that is being treated.

Myocardial Infarction: A troponin level that is twice the upper limit of the normal range or higher according to the center's laboratory, accompanied by either chest pain/symptoms consistent with ischemia or ECG evidence of ischemia.

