5.13. Subject Lost to Follow-Up

The Investigator should encourage subjects to return for the required follow-up visits. These measures are important as the clinical study objectives may not be realized if a large number of subjects are lost to follow-up (LTF).

A subject may withdraw from the clinical study at any time and should notify the Investigator in this event. If a subject refuses to return for the follow-up visits, the Investigator will attempt to obtain at least vital status and whether or not the subject has experienced a stroke or TIA. In the event of subject death, a death certificate or autopsy report should be obtained to confirm cause of death and reported on the Subject Completion / Discontinuation Form.

A subject will be considered LTF and discontinued from the study once they have missed two required follow-up visits and three documented attempts for each pending study related visit have been made by the Investigator to contact the subject.

One of the three documented attempts must include a certified (traceable) letter. The Investigator must complete the appropriate CRF (CRF Study Completion / Discontinuation Form) documenting the subject's withdrawal or discontinuation from the clinical study. The subject will be considered withdrawn once the Sponsor receives the respective CRFs.

GORE CONFIDENTIAL INFORMATION

The Investigator may also withdraw the subject from the clinical study at any time based on the Investigator's medical judgment.

The study Monitor will ensure that subject withdrawals are documented properly, discussed with the Investigator, and reported to the Sponsor

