5.14. Subject Study Completion

A subject has completed the study when he/she has completed the 3-year follow-up evaluations. Any subject that does not complete these requirements due to voluntary withdrawal, physician withdrawal, death, or any other reason will be considered as an early withdrawal. In the event of a Technical Failure (no GORE[®] Carotid Stent implanted), the subject will be followed through the 30-day visit and will be considered to have completed the study.

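### Protocol 9.1.4 has adverse events still open at death recorded as resolved, which misstates their outcome and conflicts with 9.1.3

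*Protocol*

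**What the plan says.** Protocol 9.1.4 (Subject Death) has the cause of death reported as an adverse event with death as its outcome. It then turns to the rest: "If the subject has other ongoing adverse events at the time of death", then "the outcome status of those events should be reported as 'resolved' on the AE case report form".

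Protocol 9.1.3 (Adverse Event Reporting and Coding) collects both an outcome and a resolution date for each event. An event with the status ongoing "should be assessed at each follow-up evaluation to determine if the event has resolved". At the end of participation the rule is: "Adverse events ongoing at study completion/discontinuation should be left as 'Ongoing' on the AE case report form". No exception for death is stated.

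Protocol 5.14 says that a subject who does not finish the 3-year follow-up "due to voluntary withdrawal, physician withdrawal, death, or any other reason will be considered as an early withdrawal". Protocol 5.13 asks for a death certificate or autopsy report to "confirm cause of death and reported on the Subject Completion / Discontinuation Form".

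**The concern.** Two sections of the protocol assign opposite statuses to the same event, and the one written for deaths assigns the untrue one. A bleed, an infarction or a renal injury that was still open when the subject died of something else would be held in the database as over.

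The error runs in one direction only, towards a better-looking outcome, and it falls only on subjects who died. At stake is the accuracy of a collected safety field. Anyone who later reads a listing, or tabulates outcome, could not tell from the status whether an event in a deceased subject had cleared.

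**Working it through.** No arithmetic applies. The check sets the rules side by side and then follows the field into the planned analyses.

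**1. Are the two statuses opposed?** Yes. Protocol 9.1.3 has ongoing events reassessed at each visit to see whether they have resolved, so an event is one or the other.

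**2. Does the 9.1.3 rule reach a death?** It covers events open at completion or discontinuation. Protocol 5.14 classes death before the 3-year visit as early withdrawal, and 5.13 puts death on the completion/discontinuation form. On these sections a death is a discontinuation.

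**3. Compare the instructions for one event.** Take a non-fatal event that is open on the day the subject dies of another cause.

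| Source | Status to record |
|---|---|
| Protocol 9.1.3, with 5.13 and 5.14 | Ongoing |
| Protocol 9.1.4 | Resolved |

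**4. Is the 9.1.4 entry true?** No, on its own wording. It applies only to events that it describes as ongoing at death, and then has them recorded as resolved.

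**5. What happens to the resolution date?** Protocol 9.1.3 collects it. 9.1.4 does not say what to enter, and an event that never resolved has no valid date. Sites may leave it blank, use the date of death, or do something else.

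**6. Which planned results use the field?**
- Primary endpoint (SAP 4.3): only CEC-adjudicated major adverse events count. No effect.
- 30-day major adverse events (SAP 4.4): also CEC-adjudicated. No effect.
- Adverse event rates (SAP 4.5): the numerator is subjects with at least one episode. Grouping is by MedDRA term, seriousness, relationship and timing of onset, and outcome is not among the groupings. No effect.

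**7. Where can the wrong value surface?**
- In listings or later analyses that show outcome or duration.
- In data given to the DSMB (Protocol 9.3), if outcome is included. The documents do not say whether it is.
- In the record of an unanticipated adverse device effect. Protocol 9.2 requires its duration and outcome to be documented, and such an effect could be open when the subject dies of another cause.
- In source verification. Protocol 6.9 requires accurate records, and 6.2 has monitors review case report forms and source documents. A chart showing an unresolved event would disagree with the form.

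**The case against.** The strongest reply is that 9.1.4 is a section devoted to death, placed straight after the general rule. On a normal reading the specific instruction governs deaths and the general one governs other exits. The site then has one clear instruction, and the route to 9.1.3 runs through 5.13 and 5.14, which say nothing about event coding. This has force: it would remove the operational conflict, although neither section says that an exception is intended. It does not make the entry accurate.

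A second reply is that nothing planned depends on the field. That stands in full and sets the size of the point.

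A third is that the candidate records can be found, because each such subject also has an event with the outcome death. That is true of the subjects. It does not show which of their resolved events had cleared before death, unless the resolution date reveals it, and the protocol sets no convention for that date.

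A reader might go further and infer that a disabling stroke in a subject who dies of another cause within a week would pass as minor, because Protocol 3.2.1 includes under minor stroke "A stroke that resolves completely within 7 days". The documents do not support this. That criterion is clinical and is not a form status. The CEC adjudicates against the protocol definitions, and 9.1.4 itself has the investigator obtain the medical records, death certificate and autopsy report for it. No listed endpoint or planned analysis separates minor from major stroke: any stroke counts through 30 days, and any ipsilateral stroke counts after that. Whether deficits persist beyond 7 days also cannot be observed after an earlier death, whatever the form says.

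**Conclusion.** The point holds as one of data accuracy and internal consistency. Protocol 9.1.4 instructs sites to enter a wrong outcome for events open at death. It conflicts with 9.1.3 unless it is read as an unstated exception, and on that reading the entry is still wrong.

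Its reach is narrow: the outcome and resolution-date fields of subjects who die, and whatever listings, DSMB material or device-effect documentation draw on them. The primary result and the planned adverse event rates are unchanged.

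The number of affected records cannot be stated. The documents give neither an expected mortality nor the number of events likely to be open at a death, so any count would rest on invented inputs. A reader might also infer an intent to improve the safety record. Nothing in the text suggests one, and the rule may be no more than a convention for closing records. The conclusion rests on the wording of the protocol alone. The eCRF completion instructions are not among the documents and could already handle this differently.

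**What to change.** Amend the sentence in Protocol 9.1.4 so that events unresolved at death keep the status ongoing, or are given a separate code for not resolved at death. State that no resolution date is entered. Either choice fits 9.1.3; a separate code would need to be named there too.

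Align the eCRF completion instruction. Then query the adverse event records of any deceased subjects already entered under the present rule, so that events that truly resolved before death can be told apart from those that did not.

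The cost is one protocol sentence, one eCRF instruction and a data query limited to subjects who died. The design, sample size, primary test and planned tables stay as they are.
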